9.5.1.3.3 FATIGUE SEVERITY SCALE (FSS)

The FSS is a self-report scale on which subjects are instructed to choose a number from 1 to 7 that indicates their degree of agreement with each of 9 statements about their fatigue where "1" indicates strongly disagree and "7", strongly agree. The FSS score is the sum of all responses to the 9 questions (Krupp et al., 1989). Higher scores indicate greater fatigue.

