The FSS will be further analyzed to evaluate whether lemborexant treatment affected fatigue severity in those who entered the study with clinically significant levels of fatigue. These subgroup analyses will include only those whose total FSS score was ≥ 18 at Study Baseline, which can be considered the lower threshold on the FSS for the presence of clinically significant fatigue. Analyses using the FSS analysis model will then be applied. In addition, S-plot figures will show the proportion of subjects with varying rates of response on the FSS as follows:

- Cumulative proportion of subjects with varying absolute decreases from Study Baseline in total FSS score: the x-axis will show decrease from baseline in 5-unit increments up to a ≥ 40 -unit decrease from baseline at Months 1, 3 and 6. Responder rates of -10 and -30 units will be marked on the S-Plot.
- Cumulative proportion of subjects with varying relative decreases from Study Baseline in total FSS score: the x-axis will show decrease from baseline in 10% increments up to a 100% decrease from baseline at Months 1, 3 and 6. Responder rates of -10% and -30% will be marked on the S-Plot.

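### The FSS cut of 18 for clinically significant fatigue admits subjects who disagree with every fatigue statement, and baselines of 18 to 38 cannot reach the 30-unit response mark

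*SAP*

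**What the plan says.** Protocol Section 9.5.1.3.3 asks the subject to "choose a number from 1 to 7" for each of nine statements about fatigue, with 1 for strong disagreement and 7 for strong agreement. "The FSS score is the sum of all responses to the 9 questions", and "Higher scores indicate greater fatigue".

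Protocol Section 9.7.1.6.2 and the matching synopsis text, as revised by Amendment 06, call for an FSS responder analysis confined to subjects who endorsed fatigue of clinical significance at Study Baseline. They give no numeric cut.

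SAP Section 3.4.2.4 supplies one: "These subgroup analyses will include only those whose total FSS score was ≥ 18 at Study Baseline". The SAP justifies the number only by describing it as a value "which can be considered the lower threshold on the FSS for the presence of clinically significant fatigue". No citation or derivation accompanies it. The FSS analysis model is then applied to this subgroup. S-plot figures of the cumulative response are added, with two sets of marks:

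- Absolute change: "Responder rates of -10 and -30 units will be marked on the S-Plot". The axis ends at a fall of 40 units or more.
- Relative change: "Responder rates of -10% and -30% will be marked on the S-Plot", and "the x-axis will show decrease from baseline in 10% increments up to a 100% decrease from baseline".

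**The concern.** The subgroup exists to show whether lemborexant helps people who entered the trial fatigued. A cut close to the lowest possible score may not select such people. A result reported for subjects with clinically significant fatigue would then carry a label that its definition does not support.

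The floor of the scale also limits how far a subject can fall. Anyone whose baseline is too low for a given mark is a non-responder whatever the treatment does. That lowers the responder rate in every arm and shrinks the absolute difference between arms.

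**Working it through.** **Inputs.** Nine items scored 1 to 7 and summed (Protocol 9.5.1.3.3). Cut of 18, marks of 10 and 30 units and of 10% and 30%, axis ends of 40 units and 100% (SAP 3.4.2.4). The plan derives none of these, so there is no calculation of its own to reproduce.

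**Scale limits.** Floor 9 × 1 = 9. Ceiling 9 × 7 = 63. Range 63 − 9 = 54. Midpoint 9 × 4 = 36.

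**Where 18 lies.** 18/9 = 2 per item. (18 − 9)/54 = 16.7% of the range above the floor. A subject who answers 2 to everything scores 18, and one who answers 3 to everything scores 27. Both qualify, and neither gives any answer on the agreeing side of 4. Totals of 18 to 27 can therefore arise without one endorsed statement. They need not: one 7, one 4 and seven 1s also sum to 18. The cut permits universal disagreement but does not imply it. By contrast, a total above 36 forces at least one item to be 5 or higher.

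**Reach of the marks.** From baseline B the largest fall is B − 9 units, or (B − 9)/B in relative terms. The subgroup has 63 − 18 + 1 = 46 possible totals.

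| Mark | Lowest baseline that can reach it | Qualifying totals that cannot |
|---|---|---|
| 10 units | 9 + 10 = 19 | 18 only (1 of 46) |
| 30 units | 9 + 30 = 39 | 18 to 38 (21 of 46) |
| 40 units (axis end) | 9 + 40 = 49 | 18 to 48 (31 of 46) |
| 10% | 10, since 1/10 = 10% | none |
| 30% | 13, since 4/13 = 30.8% | none |

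The largest relative fall is (63 − 9)/63 = 85.7%, so the 90% and 100% points are empty for every subject. At a baseline of 18 the limits are 9 units and 9/18 = 50%.

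**Share of subjects.** The documents give no baseline FSS distribution, and a count of totals is not a proportion of subjects. As an illustration only, assume a normal shape truncated to 9–63 with mean 27 to 45 and SD 10 or 13:

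- the cut keeps 83% to 99.7% of subjects;
- 26% to 85% of the subgroup cannot reach 30 units;
- 0.1% to 3.2% of the subgroup sit at exactly 18 and cannot reach 10 units.

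**Effect on the 30-unit comparison.** If a fraction f of each arm cannot reach the mark, the difference in rates is (1 − f) times the difference among those who can. Over the assumed range this factor is 1 − 0.26 = 0.74 down to 1 − 0.85 = 0.15.

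**The case against.** Much can fairly be said for the plan.

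- **The marks.** A reader might infer that low-baseline subjects cannot reach the planned marks in general. The table shows otherwise: only the 30-unit mark is materially affected.
- **Who is in the subgroup.** A reader might infer that the subgroup is nearly the whole sample or is made up of non-fatigued people. Neither can be shown without baseline data. Entry requires a complaint of daytime impairment and an ISI of at least 15 (Protocol 9.3.1), so many subjects may score well above 18. The SAP presents 18 as a lower bound, and a validation source may exist that it does not cite.
- **The model.** A reader might conclude that the subgroup analysis cannot answer its question. The subgroup comparison is the repeated-measures model of FSS change, which does not use the marks; the S-plots are additional figures. The floor applies to all randomised arms and does not itself favour one. The FSS analysis without the cut is also kept.
- **The plots.** The SAP does not say whether the S-plots use the subgroup. If they use all subjects, the cut does not cause the floor problem there, although baselines of 9 to 38 (30 of 55 possible totals) then cannot reach 30 units.
- **The axis.** Empty points at 90% and 100% change no estimate or test.

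These points limit the reach of the criticism. They do not answer the mismatch between cut and label: the protocol asks for endorsed fatigue, and the SAP's rule can be met by disagreeing with every item.

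**Conclusion.** Two defects stand.

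1. The cut of 18 does not implement the protocol's restriction, and nothing in the SAP justifies it. This rests on reading 4 as the neutral point of a 1-to-7 agreement scale, since the protocol labels only the two ends.
2. Baselines of 18 to 38 make a 30-unit response impossible. This is pure scale arithmetic. How many subjects it affects is unknown, and the 26% to 85% range depends entirely on the assumed distributions.

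The overlong relative axis is a presentation error.

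The FSS is an additional secondary endpoint outside the multiplicity-controlled sequence (SAP 3.3.3), so the primary and key secondary results are untouched. This is a minor-to-moderate correction to a secondary analysis. It does not show that the retained subjects lack fatigue or that the subgroup model is invalid.

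**What to change.** Amend SAP Section 3.4.2.4 before the Period 1 unblinding:

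- Replace 18 with a total above 36 (mean item score above 4), or with a cut on the 9–63 sum that has a cited source. Exactly 36 is neutral, so the cut should exclude it. Keep 18 as a sensitivity analysis if wanted.
- State whether the S-plots use the subgroup or all subjects.
- Report the 30-unit responder rate among subjects with a baseline of at least 39. This is still needed with a cut above 36, because 37 and 38 cannot reach the mark. As its denominator differs from that of the cumulative curve, give it beside the plot.
- End the relative axis at the attainable maximum of 85.7%; in steps of 10% the last usable point is 80%.

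Rescaling relative change by baseline minus 9 is not recommended as a routine repair, because it changes what the marks mean: at a baseline of 18, 30% becomes 0.3 × 9 = 2.7 units instead of 0.3 × 18 = 5.4.

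The cost is SAP wording and a smaller subgroup with wider intervals. Baseline FSS precedes randomisation, so selecting on it leaves the randomised comparison intact.

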3.5 Pharmacokinetic, Pharmacodynamic, Pharmacogenomic, and Other Biomarker Analyses

3.5.1 Pharmacokinetic Analyses

The plasma concentrations of lemborexant and its metabolites M4, M9, and M10 will be summarized using descriptive statistics by dose, time and day based on Safety Analysis Set.

A population PK approach will be used to characterize the PK of lemborexant. For this approach, PK analysis data from this study will be pooled with relevant data from Phase 1 and 2 studies, and other Phase 3 studies if available. The effect of covariates (eg, demographics, concomitant medications) on the PK of lemborexant will be evaluated. The PK model will be parameterized for oral clearance (CL/F) and volumes of distribution. Derived exposure parameters such as AUC and C_{\max} of lemborexant and any other relevant parameters will be calculated from the model using the individual estimates parameterized for oral clearance and dosing history. A separate analysis plan for the population PK analyses will be developed and finalized before the database lock.

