 - s: All other Baseline Period procedures must be completed and subject eligibility confirmed before randomization takes place and study drug is dispensed.
 - t: At each visit, subjects will be asked whether they have had a fall since the previous visit. If yes, supplemental information must be obtained to support a narrative for the event, per [Section 9.2.3](#), Adjudication Committee. (revised per Amendment 03)
 - u: PK: A single blood sample (approximately 4 mL) for plasma concentrations of lemborexant and its metabolites M4, M9, and M10 will be taken at each specified visit. The date and time of the 2 most recent doses administered before each sample will be documented.
 - v: PK sample will be collected at ET visit (not at EOS). (revised per Amendment 01)

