9.7.1.7 Pharmacokinetic, Pharmacodynamic, and Other Biomarker Analyses

9.7.1.7.1 PHARMACOKINETIC ANALYSES

The Safety Analysis Set will be used for individual lemborexant and its metabolites M4, M9, and M10 plasma concentration listings. The PK Analysis Set will be used for summaries of lemborexant M4, M9, and M10, by dose, time, and day.

A population PK approach will be used to characterize the PK of lemborexant. For this approach, PK analysis data from this study will be pooled with relevant data from Phase 1 and 2 studies, and other Phase 3 studies if available. The effect of covariates (eg, demographics, concomitant medications) on the PK of lemborexant will be evaluated. The PK model will be parameterized for oral clearance (CL/F) and volumes of distribution. Derived exposure parameters such as AUC and C_{\max} of lemborexant and any other relevant parameters will be calculated from the model using the individual estimates parameterized for oral clearance and dosing history.

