3.2 Study Subjects

3.2.1 Definitions of Analysis Sets

Safety Analysis Set: The Safety Analysis Set is the group of subjects who received at least 1 dose of randomized study drug and had at least 1 postdose safety assessment.

On-Treatment Safety Analysis Set: On-Treatment Safety Analysis Set is the group of subjects who received at least 1 dose of lemborexant and had at least 1 post dose safety assessment.

Full Analysis Set (FAS): The FAS is the group of randomized subjects who received at least 1 dose of randomized study drug and had at least 1 postdose primary efficacy measurement.

On-Treatment Full Analysis Set (FAS): On-Treatment FAS is the group of subjects who received at least 1 dose of lemborexant and had at least 1 post dose primary efficacy measurement.

6-Month Completer Analysis Set: The 6-Month Completer Analysis Set is the group of subjects in the FAS who had all efficacy assessments up to and including Month 6 (ie, Week 1 and Months 1 to 6 visits) without missing primary or key secondary efficacy assessments at any of these visits.

PK Analysis Set: The PK Analysis Set is the group of subjects who have at least 1 quantifiable lemborexant plasma concentration or its metabolites, with adequately documented dosing history.

PK/PD Analysis Set: The PK/PD Analysis Set is the group of subjects receiving either lemborexant or PBO who have efficacy or safety data with documented dosing history. In addition, subjects receiving lemborexant should have at least 1 quantifiable lemborexant concentration data point as per the PK Analysis Set.

Per Protocol Analysis Set (PP): The PP is the group of subjects who sufficiently complied with the protocol. This analysis set will include all subjects in the Full Analysis Set who sufficiently complied with the protocol during Period 1. The criteria for exclusion in this analysis set are listed below:

- Violated inclusion/exclusion criteria
- Duplicate randomization
- Missing primary efficacy assessment
- Prohibited concomitant medication

- Study drug not administered
- Incorrect study drug kit dispensed
- Non compliance of study medication

Subjects who met any of the criteria listed above will be excluded from the PP due to possible introduction of bias.

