5 CHANGES IN THE PLANNED ANALYSES

The following major changes to the statistical methods in this analysis plan were made after Amendment 03 of the Protocol was approved.

- Additional time points (ie., Months 2, 4, 5) have been included in MMRM as covariates for the primary and key secondary analysis.
- An additional safety analysis set (ie., On-Treatment Safety Analysis Set) has been defined and the safety analysis based on the On-Treatment Safety Analysis Set has been added.

The full changes to the statistical methods in this analysis plan were made in version 2.0 of the SAP from version 1.0 are detailed in [Table 1](#) at the beginning of the SAP.

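### SAP 3.5.1 bases the plasma concentration summaries on the Safety Analysis Set, although the protocol assigns them to the PK Analysis Set, and no change is declared

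*SAP*

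**What the plan says.** The protocol divides the concentration outputs between two analysis sets, in the same terms in the synopsis and in Section 9.7.1.7.1. For listings: "The Safety Analysis Set will be used for individual lemborexant and its metabolites M4, M9, and M10 plasma concentration listings". For summaries: "The PK Analysis Set will be used for summaries of lemborexant M4, M9, and M10, by dose, time, and day".

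SAP 3.5.1 describes the same summary, with the same three breakdowns, but says that the concentrations "will be summarized using descriptive statistics by dose, time and day based on Safety Analysis Set". It does not mention listings.

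SAP 3.2.1 defines both sets. The PK Analysis Set requires "at least 1 quantifiable lemborexant plasma concentration or its metabolites, with adequately documented dosing history", as in Protocol 9.7.1.2. The Safety Analysis Set is made up of subjects who "received at least 1 dose of randomized study drug and had at least 1 postdose safety assessment", with no condition on concentrations or dosing records.

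SAP Section 5 is where departures are recorded. It opens "The following major changes to the statistical methods in this analysis plan were made after Amendment 03 of the Protocol was approved", lists the extra MMRM time points and the On-Treatment Safety Analysis Set, and refers to Table 1 for the changes from SAP version 1.0 to version 2.0.

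**The concern.** A table of concentrations by dose and time is interpretable only if the dose and its timing are known. In this trial subjects take the drug at home at bedtime, and one blood sample is drawn at each PK visit. The protocol therefore requires a dosing record with each sample (Table 3 footnotes: "The date and time of the 2 most recent doses administered before each sample will be documented") and makes an adequate dosing history a condition of entry to the PK Analysis Set.

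Moving the summary to the Safety Analysis Set drops that condition, and also drops the requirement for at least one quantifiable value. At stake are the consistency of the protocol and the SAP, and the population behind the descriptive exposure table. As the texts stand, a report that follows one document departs from the other.

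**Working it through.** No arithmetic applies. The claim concerns which set is assigned to an output, so the check is to compare the texts.

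1. **Same output?** Yes. Both documents describe summaries of lemborexant, M4, M9 and M10 concentrations by dose, time and day. Only the analysis set differs.

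2. **Is the protocol sentence current?** Yes. It stands in the synopsis and in Section 9.7.1.7.1. SAP Section 1 says that the SAP is based on the protocol dated 13 Aug 2018. The revision entry of that date (Amendment 06) does not list Section 9.7.1.7.1 among the affected sections.

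3. **Does the SAP use the PK Analysis Set elsewhere?** Not for any analysis. Apart from its definition, it is named only as a cross-reference in the definition of the PK/PD Analysis Set. Otherwise it is covered only by the general count of subjects in each analysis set.

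4. **Is the change declared?** No. Neither of the two items in SAP Section 5 concerns PK, and Table 1 has no entry for Section 3.5.1.

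5. **Who is affected?** Lemborexant subjects who are in the Safety Analysis Set but not in the PK Analysis Set:
   - those with no quantifiable concentration of lemborexant or a metabolite at any visit;
   - those whose dosing history is not adequately documented.

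   Under the protocol neither group enters the summary. Under SAP 3.5.1 neither is excluded.

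6. **How large is the group?** The documents do not say. Two design features tend to keep it small. The two most recent doses are to be recorded for every sample. Subjects who stop drug but stay on study give no PK samples at later visits (Protocol 9.5.5). Missed doses and samples taken at early termination or early drug discontinuation visits (Protocol Table 2, footnote b) can still give non-quantifiable values.

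7. **In which direction?** This is not determined either. Samples with an unknown dose time can move a cell mean up or down. The effect of non-quantifiable values depends on how they are handled, which SAP 3.5.1 does not state.

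8. **Period 2.** PK sampling continues at Months 9 and 12, when former-placebo subjects take lemborexant. SAP 3.5.1 does not say under which dose their concentrations are summarised.

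**The case against.** The strongest case on the other side is that this is a mismatch of wording with little practical effect. Plasma concentrations are an exploratory endpoint, the table is descriptive, and no test depends on it. Population PK and PK/PD modelling have their own plans (SAP 3.5.1 and 3.5.2). If time means time since dose, a sample without a dose time cannot be placed in a cell under either set. All of this stands, and it limits the weight of the point. It does not remove the contradiction or the missing declaration.

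Three stronger readings are tempting, and the documents support none of them.

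- **Placebo subjects dilute the lemborexant figures.** The Safety Analysis Set does contain placebo recipients, but the summary is by dose, and SAP 3.2.1 summarises that set as treated. While on placebo, these subjects fall outside the LEM5 and LEM10 cells.

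- **Mean exposure is understated by a calculable percentage.** If a share f of the values in a cell were zero, the mean would be (1 − f) times the mean of the rest. But the documents give no f, and f is not the difference between the two sets. Both sets are defined by subject, and one quantifiable value is enough to enter the PK Analysis Set, provided the dosing history is adequate. A subject with one quantifiable sample out of several therefore stays in, together with any zeros at other visits. Changing the set would not remove f.

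- **The ratio of LEM10 to LEM5 exposure is distorted.** This needs the excluded share, or its effect, to differ between doses. Nothing in the documents indicates that it does.

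**Conclusion.** The inconsistency is real, stands in the current text of both documents, and is undeclared. Its consequence is narrow: SAP 3.5.1 as written does not exclude lemborexant subjects with no quantifiable concentration, or without an adequately documented dosing history, from the descriptive concentration summary.

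The size and direction of any effect cannot be derived from the documents. The primary and key secondary tests do not use these data, and the population PK and PK/PD analyses are planned separately. Severity is minor.

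The conclusion assumes that the SAP sentence would be programmed as it reads. If the table shells, which are a separate document, already name the PK Analysis Set, the output would be right and only the SAP text would need correcting.

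**What to change.** In SAP 3.5.1, state that individual concentrations of lemborexant, M4, M9 and M10 are listed on the Safety Analysis Set, and that descriptive summaries by dose, time and day use the PK Analysis Set. Define dose as the dose actually received, so that former-placebo subjects are counted under their lemborexant dose in Period 2. If the sponsor prefers to keep the Safety Analysis Set for the summaries, Section 5 should declare and justify the departure.

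Grouping by interval since the last documented dose is an optional refinement; it is not needed to reconcile the documents.

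The cost is one or two sentences. Both sets are already defined, the dose times are already to be collected, and no new data or analysis is needed.

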3.5.2 Pharmacodynamic, Pharmacogenomic, and Other Biomarker Analyses

The PK/PD relationship between exposure to lemborexant and the efficacy variables including but not limited to sSOL, sSE, and sWASO, and the safety variables including but not limited to morning sleepiness and frequently occurring TEAEs, will be explored graphically. Any emergent PK/PD relationships will be evaluated by population PK/PD modeling. The population PK/PD analysis plan will be described and results will be reported in a separate document.

Population PK and PK/PD analyses will be performed using NONMEM Version 7.2 or later.

3.6 Safety Analyses

[figure not shown]
Evaluations of safety will be performed on the relevant Safety Analysis Set and On-Treatment Safety Analysis Set, as appropriate. All safety analyses will be performed based on observed data using tabulation or descriptive statistics only.

No hypothesis testing will be performed for safety analyses

[figure not shown]
